 - To assess whether placement of a postoperative drain is associated with earlier detection of collections and anastomotic leak.
 - To examine when drains can be safely removed.
 - To explore the clinical decision-making process for drain placement after colorectal surgery.
 - To characterise the incidence of complicated postoperative collections and their clinical management in colorectal surgery in an international cohort.

4. Project Timeline

Data collection will take place between 3rd February 2020 and 26th April 2020 during the following four predefined 14-day data collection periods.

- **Period 1:** 08:00 AM 3 Feb 2020 to 08:00 AM 17 Feb 2020 (+ 30 Day Follow-up)
- **Period 2:** 08:00 AM 24 Feb 2020 to 08:00 AM 09 Mar 2020 (+ 30 Day Follow-up)
- **Period 3:** 08:00 AM 16 Mar 2020 to 08:00 AM 30 Mar 2020 (+ 30 Day Follow-up)
- **Period 4:** 08:00 AM 13 Apr 2020 to 08:00 AM 27 Apr 2020 (+ 30 Day Follow-up)

An extra period may be opened at the discretion of the steering committee to allow for the participation of centres that encountered difficulties in obtaining the necessary ethical approvals:

- **Period 5:** 08:00 AM 27 Apr 2020 to 08:00 AM 11 May 2020 (+ 30 Day Follow-up)

At each hospital, one mini-team per period will collect data on eligible patients admitted over a 14-day period. Data on 30-day outcomes after the day of surgery will also be collected. The deadline for uploading collected data onto REDCap is 30th June 2020.

Patients should be included if their operation started (defined as 'knife-to-skin' time) within the time period during the data collection periods as specified above.

One mini-team of up to three collaborators can take part in each 14-day period. Multiple mini-teams can participate at each centre, but no more than one team per period at the same centre. To be listed as PubMed-citable collaborators, centres are required to participate in at least one data collection period.

5. Centres

- COMPASS is open to any hospital in the member countries of the European Society of Coloproctology (ESCP), the Royal Australasian College of Surgeons (RACS) and South African centres, which routinely perform elective or emergency colorectal surgery. Participation of centres from other countries will be considered on a case-by-case basis.

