- Time (measured in whole days) until drain removal and drain output (quantity and contents) on day of removal. Daily output will be calculated adding up the volumes drained in the 24 hours prior to the morning ward round. Contents are defined as serous fluids (with or without blood staining), frank blood, purulent and faecal.
- Overall 30-day adverse event rate as defined by the Clavien-Dindo scale of postoperative complications (25) and length of stay (days).

- ▲ Day of surgery is defined as Post-operative Day (POD) 0. The day after surgery is therefore defined as POD 1 and day 10 after surgery as POD 10. ▲

8. Measuring drain output

Drain output (volume and contents) should be assessed daily until removal or for the first ten days after surgery (Day 0: day of surgery – Day 10).

Strategies to record drain output and day of drain removal

- Speaking to ward staff, including doctors and nurses
- Reviewing patient notes daily, particularly drain charts
- Participating in daily ward rounds and doctor reviews

Remember: recordings of drain output must correspond to the entire day (8am to 8am). It is advised that you collect data one day in retrospect to capture all relevant data.

9. Covariates

Data will be collected on audit standards, and confounding factors for risk of intra-abdominal postoperative complications to permit accurate risk adjustment of outcomes. Without appropriately adjusting for risk factors, it is likely that any findings would be biased and unable to be appropriately analysed on a national scale. Data will **not** be analysed at a surgeon-level or centre-level. A full list of required data fields is available in Appendix A, and on the REDCap database.

10. Follow-up

Patients will be followed for 30 days after surgery. All secondary outcome measures will be recorded if they occurred at any point from postoperative Day 0 (day of surgery) to Day 30.

No change to routine follow up should take place. Collaborators should be proactive in identifying follow up data, but this should be done within the limits of routine follow up.

Strategies for follow-up include:

- Regularly reviewing patient notes to identify in-hospital complications.
- Participating in daily ward rounds and doctor reviews.
- Reviewing clinic notes and clinic letters, if seen in clinic by 30 days.
- Checking electronic systems and handover lists for re-admissions.
- Checking for emergency department re-attendances.

11. Data Analysis & Sample Size

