Appendix A: Data Dictionary

Please use the case report form together with this Data Dictionary to facilitate data collection

Preoperative data points	Required data (definition / comment)
Patient age	Years (whole years at the time of operation)
Patient gender	Male / Female
Patient ASA grade	Grade I-V (Full ASA classification available at: https://www.asahq.org/resources/clinical-information/asa-physical-status-classification-system).
Smoking status	Current (includes those who stopped smoking within 6 weeks), Previous , Never .
Patient height	Meters (record to two decimal places)
Patient weight	Kilograms (record to one decimal places)
Body Mass Index (if either weight or height unknown)	Underweight (<18.5), Normal range (18.5-24.9), Overweight (25-30), Obese (>30).
History of abdominal surgery	Yes / No
Pre-existing abdominal stoma	Yes – colostomy / Yes – jejunostomy or ileostomy / No stoma
History of ischaemic heart disease	Yes (Myocardial infarction or Angina) / No
History of congestive heart failure	Yes / No

History of cerebrovascular disease	Yes (transient ischemic attack or stroke) / No
History of diabetes mellitus	Yes (Type 1) / Yes (Type 2) / No
Control of diabetes mellitus	IF diabetes mellitus present Yes, insulin controlled / Yes, tablet controlled / Yes, diet controlled / No
Last pre-operative blood test values	Haemoglobin (grams / litre) / White Cell Count ($\times 10^9$ / litre) / estimated Glomerular Filtration Rate (ml / min) / C Reactive Protein (milligrams / litre).
History of immunosuppression	HIV (antiretroviral therapy, no/unknown), Steroids (yes: oral, intravenous or topical e.g. prednisolone, fludrocortisone, dexamethasone, no), Other immunosuppressive drug (yes, e.g. azathioprine, methotrexate, biologic agents, no), Chemotherapy (yes, current chemotherapy or if the last cycle was within 12 weeks of operation, no).
Operative data points	Required data (definition / comment)
Underlying pathology/indication	Malignancy / Inflammatory bowel disease / Diverticular disease / Bowel ischaemia / Small bowel obstruction / Large bowel obstruction / Other benign
Perforated bowel	Yes / No

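### The immunosuppression row in Appendix A codes topical steroids with systemic ones, gives steroids no look-back window and gives untreated HIV no distinct code; the effect on risk adjustment is small and the remedy nearly free

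*Protocol*

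**What the plan says.** Protocol, Appendix A (Data Dictionary), has one row on history of immunosuppression with four separate items:

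- Steroids: "Steroids (yes: oral, intravenous or topical e.g. prednisolone, fludrocortisone, dexamethasone, no". Three routes share one answer, and no window, dose or duration is given.
- HIV: "HIV (antiretroviral therapy, no/unknown". There are two options only.
- Other drugs: "Other immunosuppressive drug (yes, e.g. azathioprine, methotrexate, biologic agents, no". This item has no window either.
- Chemotherapy: "Chemotherapy (yes, current chemotherapy or if the last cycle was within 12 weeks of operation, no". This item does have a window.

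In the same table, smoking also carries a time rule: "Current (includes those who stopped smoking within 6 weeks".

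Section 9 (Covariates) says confounding factors are collected "to permit accurate risk adjustment of outcomes", warns that unadjusted findings would probably be biased, and points to Appendix A for the fields. It does not name immunosuppression as a model term, and it does not say whether the four items will be combined. One secondary aim in section 3 is to assess whether a drain is associated with earlier detection of collections and anastomotic leak.

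**The concern.** A covariate collected for risk adjustment should separate patients who carry the risk from those who do not. Three features of this row work against that.

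First, the steroid item counts topical use as exposed. No reading of the row avoids this. If topical-only use does not carry the risk that systemic use does, the indicator mixes exposed with effectively unexposed patients.

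Second, the steroid item has no window. Data collectors at some 300 anticipated centres must decide for themselves whether a past course counts. Chemotherapy and smoking show that timing was considered elsewhere in the table.

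Third, a patient with known HIV who is not on therapy has no option of their own. If the second option means no HIV, this patient has no place. If it means no therapy, they share a code with uninfected patients and those of unknown status. On either reading the information is lost. Section 5 opens the study to "South African centres, which routinely perform elective or emergency colorectal surgery", so the case should be foreseen.

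At stake is how well steroid use and HIV are controlled when drained and undrained patients are compared. The quality checks would not reveal the problem. The validator in section 14 re-collects the key fields under the same definitions, and an unknown HIV status is entered as a valid answer and so passes the completeness threshold of more than 95%.

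**Working it through.** The protocol gives no figure on this point, so there is none to reproduce. The coding features are read directly from the text. The calculation below shows only how large the consequence might be.

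**Inputs, all assumed:**
- 5% of patients are on current systemic steroids, with a true odds ratio (OR) of 2.5 for a collection.
- The collection risk without systemic steroids is 10%.
- Topical or remote use has no effect and adds a further 5% or 10% of patients to the recorded yes group.
- 35% of patients not on systemic steroids are drained. The background section gives 35% as the share of centres that routinely drain most patients, which is a different quantity, so this too is an assumption.
- The steroid-drain OR is 1.5 or 3, and the true drain OR for a collection is 1.

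**Step 1: dilution of the steroid indicator.**
- Odds at 10% = 0.10/0.90 = 0.1111. Times 2.5 = 0.2778. Risk in systemic users = 0.2778/1.2778 = 21.7%.
- With 5% extra, half of the recorded yes group is truly exposed: (21.7 + 10)/2 = 15.9%. OR = (0.1587/0.8413)/0.1111 = 1.70.
- With 10% extra, one third is truly exposed: (21.7 + 2×10)/3 = 13.9%. OR = (0.1391/0.8609)/0.1111 = 1.45.

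**Step 2: effect on the drain comparison.** The estimate is the Mantel-Haenszel OR, Σ(a·d/n) / Σ(b·c/n), stratified by the recorded steroid answer. Here a and b are drained patients with and without a collection, and c and d are undrained patients with and without one.

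Worked case: 5% extra, steroid-drain OR 1.5, expected counts per 5000 patients. The drain rate in systemic users has odds 1.5 × 0.35/0.65 = 0.8077, which is 44.7%.

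| Recorded steroid | a | b | c | d | n | a·d/n | b·c/n |
|---|---|---|---|---|---|---|---|
| Yes | 33.03 | 166.17 | 46.31 | 254.48 | 500 | 16.81 | 15.39 |
| No | 157.5 | 1417.5 | 292.5 | 2632.5 | 4500 | 92.14 | 92.14 |

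OR = (16.81 + 92.14)/(15.39 + 92.14) = 108.95/107.53 = 1.013.

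All four cases:

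| Steroid-drain OR | No adjustment for steroids | Adjusted, 5% extra | Adjusted, 10% extra |
|---|---|---|---|
| 1.5 | 1.025 | 1.013 | 1.018 |
| 3 | 1.070 | 1.037 | 1.049 |

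The truth is 1 throughout. The excess that remains after adjustment is about half of the unadjusted excess with 5% extra (0.013/0.025 and 0.037/0.070) and about 70% with 10% extra (0.018/0.025 and 0.049/0.070).

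**Step 3: a different set of assumptions.** Take systemic use 5–10%, topical or remote-only use 2–10% of the rest, true steroid OR 1.5–2.5, steroid-drain OR 1.5, baseline collection risk 5% and baseline drain rate 35%. The recorded steroid OR falls from 2.5 to 1.49–2.26, or from 1.5 to 1.17–1.42. The adjusted drain OR is 1.003–1.025, against 1.010–1.048 without adjustment.

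**Step 4: untreated HIV.** The documents give no prevalence. With an assumed 0.2–5% prevalence and 10–30% untreated, the number in the anticipated 5000 runs from 5000 × 0.002 × 0.10 = 1 to 5000 × 0.05 × 0.30 = 75.

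**The case against.** The strongest reply is that no estimate the protocol promises is materially affected. No stated aim estimates the steroid coefficient, so its dilution matters only through the drain comparison, where the bias is a few hundredths of an odds ratio. Even a perfectly recorded steroid field would move the drain OR by only about 0.03 to 0.07. The primary outcome, adherence on drain insertion, does not use the field. All of this stands, and it sets the severity.

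Several stronger readings are tempting, and the document does not support them:

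- *Steroids given at any time count as exposed.* This is not written. The row is silent on timing, and the history label is also used for diabetes and heart failure. The defect is an undefined window, which permits that reading without requiring it.
- *One covariate is misclassified in both directions.* The steroid item may over-count and the HIV item may under-count, but they are separate items. A two-way error in a single factor arises only if they are pooled, and nothing says that they will be.
- *Immunosuppression is a planned model term.* Section 9 and Appendix A make this likely, but no model is shown, and the choice of terms may lie in an analysis plan not at hand.
- *The loss cannot be repaired.* Collectors are told to use the dictionary together with a case report form, which is not shown and may be clearer. What can be said is that an analysis plan cannot restore route, timing or HIV status if they were never collected.

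The HIV limb is also thin on numbers. South African centres are eligible, but the sample estimate in section 11 counts only the UK, Europe and Australasia. The second HIV option may mean no or unknown antiretroviral therapy, in which case the fault is an ambiguous, merged category.

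**Conclusion.** The concern holds as a minor weakness in data definition. Three things rest on the text alone: topical steroids are coded as exposed together with oral and intravenous use; steroids have no window although chemotherapy in the same cell does; and known untreated HIV has no distinct code.

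The consequence is conditional on these items being used for the adjustment that section 9 describes. A diluted steroid indicator would then control only part of the confounding it is collected for. A true OR of 2.5 would be recorded as about 1.45 to 1.70, and the adjusted drain OR would be about 1.01 to 1.05 when the truth is 1. These figures rest wholly on the assumed prevalences, risks and associations and on topical or remote use having no effect; the documents supply none of them. The number of patients affected by the HIV coding cannot be derived from the protocol. The primary adherence rate is untouched.

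**What to change.** In Appendix A and the matching REDCap options:

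1. Record steroid route as separate options: systemic (oral or intravenous), topical only, none. This keeps topical use in the data and leaves its handling to the analysis.
2. State a pre-operative look-back window for steroids and for other immunosuppressive drugs, as the same cell already does for chemotherapy ("current chemotherapy or if the last cycle was within 12 weeks of operation").
3. Split HIV into on antiretroviral therapy, HIV not on therapy, no HIV, and unknown, so that unknown status is visible and is not absorbed into a valid negative.

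The cost is a few more drop-down options, a line of wording and slightly more collector effort. No additional data source should be needed.

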- All participating centres are required to register the study according to local regulations. Evidence of successful registration must be uploaded onto REDCap prior to commencement of data collection. Centres will not be allowed to upload patients' data onto REDCap without evidence of successful registration of the study.
- In the UK, COMPASS has been designated an audit of practice. Internationally, individual study investigators are responsible for ensuring the correct audit, ethical or departmental approval has been achieved prior to commencing data collection (this can be registered as an audit or service evaluation, if appropriate).
- Following the conclusion of the study, it is recommended that mini-teams at each centre present the study findings to their hospital's surgery departments as part of the audit process.

Providing feedback on the project's findings to your department's clinicians is an essential step for improving care. Presenting local results will help you to develop your presentation skills & CV.

6. Eligibility criteria

Summary: Consecutive adult patients (≥ 18 years of age) undergoing emergency or elective colorectal surgery through any operative approach should be included.

- **Inclusion criteria**

Age	Age 18 years or above.
Procedure	Any formation of colostomy/ileostomy, resection of large bowel, or reversal of stoma (See Appendix B for full list).
Urgency	Emergency and elective procedures.
Technique	Open, laparoscopic, laparoscopic converted, robotic, robotic converted procedures are all eligible.

- **Exclusion criteria**

Procedures	
 • Appendicectomy (unless procedure involves a right hemicolectomy) • Transanal surgery - e.g. TaTME, TEMS, TAMIS, Altemeier's procedure. • Primarily urological procedure - e.g. ileal conduit. • Primarily gynaecological procedure - e.g. Hartmann's during ovarian cancer surgery • Primarily vascular procedure - e.g. bowel resection during AAA repair. • Diagnostic laparoscopy or laparotomy without resection of colon or rectum • Inguinal, incisional or femoral hernia, without resection of colon or rectum • Surgery involving major multi-visceral surgery – e.g. pelvic exenteration
Re-operation	Each individual patient should only be included in the COMPASS study once. Return to theatre during the same admission or follow up is regarded as a complication .

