Appendix B: Included procedures

- Ileocolic resection
- Right hemicolectomy
- Extended right hemicolectomy
- Transverse colectomy
- Left hemicolectomy
- Sigmoid colectomy (including Hartmann's Procedure)
- Anterior resection
- Sub-total colectomy
- Total colectomy
- Pan-proctocolectomy
- Completion proctectomy
- Closure/reversal of stoma (ileostomy or colostomy)
- Formation of stoma (ileostomy or colostomy)

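### One undefined field mixes underlying disease with obstruction, so a single entry for an obstructing cancer or stricture loses one fact needed for risk adjustment

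*Protocol*

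**What the plan says.** Among the operative data points in Appendix A (Data Dictionary) is one item labelled "Underlying pathology/indication". Its options are "Malignancy / Inflammatory bowel disease / Diverticular disease / Bowel ischaemia / Small bowel obstruction / Large bowel obstruction / Other benign". It carries no definitions, no order of precedence and no statement on whether more than one option may be chosen. The next item, "Perforated bowel", is a separate Yes/No field. Obstruction has no such field.

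Section 6 makes eligible "Any formation of colostomy/ileostomy, resection of large bowel, or reversal of stoma (See Appendix B for full list", and Appendix B lists "Closure/reversal of stoma (ileostomy or colostomy" among the included procedures. No option of the pathology item refers to stoma closure.

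Section 9 (Covariates) gives the purpose of the fields: "Data will be collected on audit standards, and confounding factors for risk of intra-abdominal postoperative complications to permit accurate risk adjustment of outcomes". It adds that unadjusted findings would probably be biased, and it refers to the appendix: "A full list of required data fields is available in Appendix A".

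**The concern.** A categorical covariate does its work only if each patient has one correct value. Here malignancy, inflammatory bowel disease and diverticular disease are causes, while small and large bowel obstruction are ways in which those causes present. The label itself joins two questions. Data collectors at an anticipated 300 centres (150 in the UK and 150 elsewhere, Section 11) will have to choose between two correct answers without a rule.

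The secondary aims are what is at stake. Section 3 asks whether a drain is associated with earlier detection of collections and leaks. Obstruction could plausibly influence both the decision to drain and the risk of a collection. If some obstructed patients appear only under their disease, adjustment for obstruction is incomplete. If others appear only under obstruction, adjustment for disease is incomplete. An analysis plan written later cannot restore a fact that was never recorded.

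**Working it through.** No figure in the protocol can be reproduced for this point, so the check is mainly a comparison of text.

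**Step 1: apply the option list to typical eligible patients, one entry allowed.**

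| Patient | Options that fit | What one entry loses |
|---|---|---|
| Obstructing large bowel cancer | Malignancy; large bowel obstruction | The obstruction or the cancer |
| Obstructing diverticular stricture | Diverticular disease; large bowel obstruction | The obstruction or the disease |
| Obstructing stricture in inflammatory bowel disease | Inflammatory bowel disease; small or large bowel obstruction | The obstruction or the disease |
| Stoma closure after cancer surgery | Malignancy; other benign | The original disease, if other benign is entered |

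**Step 2: look for the lost fact elsewhere in Appendix A.**
- Operative urgency partly marks emergency presentation, but does not separate obstruction from other emergencies.
- Perforation, contamination and stoma formation are separate fields. They may capture part of the related risk but do not record obstruction.
- The primary-operation field identifies every stoma closure. It does not give the disease behind the stoma.
- Nothing separates an obstructing cancer from a benign obstruction once only large bowel obstruction has been entered.

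**Step 3: try the reading under which no conflict arises.** The residual option, other benign, could imply that the obstruction codes mean benign obstruction, so that malignancy always takes precedence. The protocol does not say so. On that reading obstruction in cancer patients is never recorded, and inflammatory and diverticular strictures still have two codes.

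**Step 4: scale, by assumption only.** Section 11 anticipates about 5000 patients. If patients without a unique code, stoma closures included, made up 5% to 20%, that would be 0.05 × 5000 = 250 to 0.20 × 5000 = 1000 records. The protocol gives no case mix, so the true share is unknown.

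**Step 5: how incomplete adjustment would act, as an illustration.** All inputs are assumptions: obstruction doubles the risk of a collection, is present in 20% of drained and 10% of undrained patients, and half of it in each group is coded as the disease.
- No adjustment: (1 + 0.20)/(1 + 0.10) = 1.091.
- Patients not coded as obstructed: hidden prevalence is 0.10/0.90 = 0.111 (drained) and 0.05/0.95 = 0.053 (undrained), so the bias factor is 1.111/1.053 = 1.056.
- Patients coded as obstructed: all are obstructed, so the factor is 1.
- Both strata pooled by Mantel-Haenszel, equal group sizes (a further assumption): numerator 0.90 × 1.111 × 0.95/1.85 + 0.10 × 2 × 0.05/0.15 = 0.5135 + 0.0667 = 0.5802. Denominator 0.95 × 1.053 × 0.90/1.85 + 0.05 × 2 × 0.10/0.15 = 0.4865 + 0.0667 = 0.5532. Ratio 1.049.

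The like-for-like comparison is therefore about 5% against 9%, both for the whole cohort. On the same inputs the range runs from 1.000 (all obstruction coded as obstruction) to 1.091 (none of it). Adjustment for urgency and the other fields could reduce this further. The illustration shows the mechanism and is not an estimate for this study.

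**The case against.** The strongest objection is that single choice is inferred. Appendix A tells collectors to use the case report form alongside the dictionary, and that form is not shown. In the same table slashes also separate the blood results, which are all recorded together, and the immunosuppression item has a singular label but holds several answers. If the form allows several ticks, the obstruction problem largely disappears. This stands as a limit, so the point is conditional. Single choice is still the more natural reading. The blood results carry their own units and the immunosuppression items their own answers, whereas this list is bare and ends in a residual category.

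Partial safeguards also exist. Section 14 has validators re-collect key risk-adjustment fields against an accuracy target above 98%, so inconsistent coding could surface. Whether this field is among them is not stated. Conflicts are settled by discussion, with no rule for choosing between two correct codes.

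A reader might go further in four ways that the protocol does not support:
- That a planned model covariate is already misclassified. Section 9 names no model and no covariate. The role of this field is inferred from the reference to Appendix A and from its being neither an audit standard nor an outcome.
- That stoma closures are lost to the analysis. The procedure field identifies them, so an analyst can separate them.
- That a malignant/benign comparison is compromised. None is planned.
- That a known amount of bias follows. Every input in the illustration is assumed, and setting 6% in one stratum against 9% in the whole cohort would compare unlike quantities.

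**Conclusion.** The point holds, conditional on the item being completed as a single choice. On that reading obstructing cancers and strictures have two valid codes, teams will code them inconsistently, and one of two relevant facts is lost with no other field to recover it. This weakens the adjustment that Section 9 intends for the secondary drain comparisons. The primary outcome, adherence on drain insertion, is not affected. The stoma-closure part is minor: only the underlying disease is ambiguous, not the identity of the cases. The documents do not allow an estimate of the number of patients or of the bias. The change is worth making because it is cheap and has to be in place before data are collected.

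**What to change.** Split the item into two fields:
1. Underlying disease: malignancy, inflammatory bowel disease, diverticular disease, ischaemia, or other benign.
2. Obstruction at presentation: none, small bowel, or large bowel, kept separate in the same way as the field "Perforated bowel".

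Add one dictionary line stating that for a stoma closure the underlying disease is the one that led to the stoma. No extra indication code is needed, because the procedure field already identifies closures.

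The cost is one extra REDCap field per patient and one line of text. A precedence rule on the existing item would be cheaper and would make coding consistent, but it would still discard either the disease or the obstruction. If the case report form already permits several entries, the dictionary should say so.
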